## RESEARCH DESIGN AND METHODS

### Aim 1 Effect of REVAMP management compared to in-person care on functional outcomes

Study population and enrollment of participants. Veterans (n=356) referred to one of the sleep centers for evaluation of OSA will be recruited. Men and women will be included with no restrictions based on race and ethnicity. We will target women's clinics to enhance the recruitment of women. Healthcare providers submitting referrals will be asked on the CPRS consult form whether or not the patient is interested in participating in the study. Interested patients will be contacted by phone by the study coordinator to explain the study and determine if they have internet access and are eligible based on the inclusion/exclusion criteria. Eligible patients interested in participation will be scheduled to meet with the study coordinator to obtain signed informed consent. Patients who are ineligible or decline to participate will be scheduled for a routine initial clinic appointment. Enrolled participants will be given the uniform resource locator (url) address to the REVAMP website and a user name and temporary password. The participant's primary care provider will be informed that his/her patient is enrolled in the study and that all clinically indicated care should continue to be provided.

Eligibility criteria and enrollment. Veterans must meet the following inclusion criteria prior to enrollment:

1. Age  $\geq$  18 years and enrolled at one of the participating VAMCs
2. Referral to one of the participating sleep centers for evaluation of suspected OSA
3. Access in the home to the internet, e-mail, and phone on all days
4. *Living within a 45 miles radius of the clinical site so that participants randomized to in-person delivery of care will be able to travel to and from the sleep center*
5. Fluent in English as assessed on the initial phone contact

Individuals will be excluded from the study for the following reasons:

1. Unable or unwilling to provide informed consent and complete required questionnaires
2. Previous diagnosis of OSA, central sleep apnea ( $\geq$  50% of apneas on diagnostic testing are central apneas), Cheyne-Stokes breathing, obesity hypoventilation syndrome, or narcolepsy
3. Previous treatment with PAP, non-nasal surgery for OSA, or current use of supplemental oxygen
4. A clinically unstable medical condition in the previous 2 months as defined by a new medical diagnosis (e.g., pneumonia, cardiac disease, thyroid disease, depression or psychosis, cirrhosis, cancer, etc.)
5. Individuals who regularly experience jet lag or irregular work schedules over the previous 3 months
6. Women who are pregnant or women who are sexually active and of child-bearing age who are not using some form of contraceptive
7. *Unable to perform tests due to visual (inability to read the consent form) or hearing (unable to have a phone conversation) impairment, or unable to perform activities of daily living*

Participants will complete the following baseline questionnaires on the website: FOSQ-10, EES, SF-12, CES-D, EQ-5D (including the EuroQol feeling thermometer), and medical service use not captured by their electronic medical record (Table 2 and Appendix 3). The Charlson comorbidity index will be used to determine if health status predicts which patients are good candidates for REVAMP management.

To monitor for possible selection bias, all potential participants will be tracked to determine the number who agree to be contacted, the number who provide informed consent, the criteria that excluded an individual's participation, and the reasons why participants were unable to complete the protocol. Post-hoc analysis will compare patient characteristics at baseline to assess for any differences across groups and sites. Following completion of the baseline questionnaires, the CES-D score will be reviewed by a member of the research team who is not involved with delivery of care. The participant's primary care provider will be notified if the CES-D score is greater than 24, indicating the presence of severe depression. These participants will be allowed to continue in the study since all participants with OSA will receive APAP treatment and this intervention has been shown to improve depression. To assess for any medication changes that might affect functional outcomes, a list of the participant's medications, with their dosage and frequency, will be obtained from the patient and the patient's medical record during the first 3 months of PAP treatment.

All participants will complete the website questionnaires in order to standardize collection of our functional outcomes. Practitioners in both arms will not have access to the responses to the patient satisfaction questionnaires (WAI-SR and CSQ-8). The other questionnaire responses of the participants randomized to REVAMP management will be available to the practitioners performing the phone clinic evaluations. Enrolled subjects assigned to the in-person arm will only have access to the website's questionnaires but none of its other features. They will be informed that a research staff member will contact them to schedule their first clinic appointment. None of the questionnaires they complete on the website will be shared with their practitioners. At the time of their in-person clinic visits, these participants will complete the questionnaires that are routinely used as a part of the clinical site's usual care. That information will not be collected for analysis.

**Table 2.** Data collection and action schedule for all participants

Measures & Procedures	Baseline assessment	Initial clinical assessment	AutoCPAP set-up	1-week phone FU	1-month FU assessment	3-month FU assessment
	Week 0	Week 2-4	Week 8	Week 9-12	Week 12	Week 20
Eligibility criteria	In-person					
Informed consent	In-person					
Patient characteristic questionnaire	website					
Functional & QOL questionnaires†	website				website	Website Δ
Therapy process indicators‡		website		website	website	Website Δ
Clinical assessment*		In-person vs phone		Phone	In-person vs phone	In-person vs phone
APAP set-up			DME			
APAP adherence*				Wireless	Wireless	Wireless

DME = home health care company; FU=follow-up; QO =quality of life; Δ=performed every 3 months thereafter to the end of data collection

\* Subjects randomized to in-person management will have in-person clinic evaluations in the sleep center and subjects randomized to REVAMP management will have phone clinic sessions. APAP adherence in both groups will be obtained by wireless modem.

[figure not shown]
† Functional & QOL questionnaires: FOSQ-10, ESS, SF-12, CES-D, and EQ-5D; ‡ Therapy process indicators: WAI, CSQ-8 (performed within 1-week following each encounter)

**Participant randomization.** Upon completing baseline questionnaires, a computer-generated, blocked randomization scheme in the REVAMP program will automatically allocate eligible participants into one of two groups: *REVAMP management versus in-person management*. Randomization at each site will be programmed by SAS module Proc Plan. Block size at each site will be six subjects so that among each block of six randomized individuals, exactly three will be assigned to each group in a random order. Investigation and management of the two arms of care will be conducted over equal time periods.

**REVAMP pathway.** Following completion of the website questionnaires and the HST, REVAMP participants will be scheduled for an initial phone interview with the *sleep specialist (MD or NP)* (Fig 4). The practitioner will review the results with the subject. *Using the criteria required by the Center of Medicare and Medicaid Services, participants with AHI  $\geq 15$  events/hr and subjects with  $5 \leq AHI < 15$  who have OSA-related symptoms will be diagnosed with OSA.* Those interested in PAP treatment will be prescribed an APAP unit with wireless modem. Subjects with OSA who are found on follow-up to require bilevel PAP and/or supplemental oxygen will continue to participate in Aim 1. Participants testing negative for OSA will be offered usual clinical care to further evaluate their sleep-related symptoms. Participants with a diagnosis of central sleep apnea/Cheyne-Stokes respiration

(CSA/CSR) will be referred to a sleep physician and PSG testing. *Participants without OSA on HST and participants with CSA/ CSR will not be included in the Aim 1 modified intent to treat analysis set but will be included in the primary analysis set of Aim 2 and Aim 3.*

The wireless modem on the home PAP unit sends PAP data daily to the manufacturer's server which in turn exports the data daily to the REVAMP website. The website displays the following information in an easily understandable format: hours of use, amount of air leak, and AHI (Fig. 2). Participants and practitioners can view the data on the REVAMP website. Participants will be instructed to review their results on the website daily. The number of times a subject logs into the website will be tracked.

Following the first week of PAP treatment, a therapist with at least one year of experience managing patients with OSA will phone the participant. Using a standardized protocol, the therapist will evaluate the participant's response to treatment, inquire if any barriers are limiting PAP use, and provide advice on how to overcome those problems (see *Appendix 4*). The therapist will encourage the participant to review his/her PAP data on the website. The participant will be scheduled for 1- and 3-month follow-up phone calls with the therapist. Additional phone calls are allowed as clinically indicated and will be tracked. The therapist will have the option of consulting with the sleep specialist (MD or NP). Upon consultation, if it is felt that the problem cannot be addressed by phone, the participant will be scheduled for an in-person clinic appointment with the physician. The type, number

and duration of all encounters will be recorded in case report forms. All phone clinic sessions and other patient encounters will be documented in the participant's electronic medical record.

REVAMP has a secure message system that sends e-mail and text messages to the participant alerting him/her to login to the website to view a message. The REVAMP website will use this feature to remind the participant to complete questionnaires, view their PAP data, and keep scheduled phone clinic appointments.

*In-person management.* Participants in the in-person arm will be scheduled to meet with the sleep therapist for in-person set-up instructions for HST. Following HST, a sleep specialist (MD or NP) will conduct the initial in-person clinic evaluation. Participants diagnosed with OSA (using the same criteria detailed above for the REVAMP pathway) who are willing to start PAP treatment will be prescribed APAP. Sleep therapists with at least one year of experience managing patients with OSA will perform the follow-up clinic evaluations. Participants will receive a 1-week phone call and be scheduled for 1- and 3-month in-person follow-up clinic visits. Additional phone calls and clinic visits will be allowed as clinically indicated. The type, number and duration of all encounters will be monitored and documented in the participant's electronic medical record.

Other than the above requirements, each site will conduct in-person management according to their usual clinical practice. The decision to allow each site to conduct its current in-person clinical care will make our findings more generalizable. Not having to replicate the exact same conditions for in-person management at the sites reduces the cost of the project. We realize that allowing these differences at the 3 sites raises the possibility of a site-related bias. We will assess this by including site as a covariate in the analysis models.

*Home sleep testing and polysomnogram.* Participants in both the in-person and REVAMP arms will have an HST as their first diagnostic test, but their practitioners will have the ability to order an in-lab PSG when clinically indicated. A technically acceptable HST will require at least a 3 hr recording of oxygen saturation and one respiratory signal. Recordings that are technically inadequate will be repeated once. If the repeat HST is not of acceptable quality, the participant will be scheduled for an in-lab PSG performed according to AASM recommended guidelines. To reduce the possibility of a false negative HST result, participants with an AHI < 5 events/hr on initial HST will repeat the study. Participants with two negative HSTs will be advised that they may still have OSA and, if clinically indicated, can be offered the option of an in-laboratory PSG.

The clinical sites will use a type 3 portable monitor that records nasal pressure, rib cage and abdominal movement, pulse oximetry, and body position. Two of the sites use the T3 monitor (Nox Medical) and the third site uses Nomad, Nihon Kohden. We will control for diagnostic bias by ensuring that the sites record identical channels, at an identical sampling frequency. The monitor will be distributed to participants in the REVAMP arm without in-person set-up instructions, and they will be directed to the REVAMP website to review a video on OSA and PAP treatment developed by the American Sleep Apnea Association and a step-by-step instructional video and brochure explaining HST set-up (Appendix 2). Postal materials will be provided to mail the monitor back to the sleep center using a carrier that allows tracking of the package. Participants randomized to in-person management will be scheduled to meet with a technologist at the sleep center to receive in-person instructions on how to perform the test. During the visit, the subject will be shown the videos and provided with the set-up brochure (Appendix 2). The therapist will explain how to operate the monitor, demonstrate placement of the sensors, and answer the participant's questions. The patient will be given the option of returning the monitor by mail or in-person. Participants in both arms will be provided a 24/7 phone number to contact an on-call PSG technologist at the site's sleep center with any questions about the set-up.

*Scoring of sleep testing.* The HSTs and PSGs will be scored by an experienced PSG technologist at the respective clinical site and interpreted by a sleep specialist at that site who is blinded to randomization arm and not involved with participant management. The decision not to have centralized scoring of the sleep tests increases the "real world" nature of the project, improves turn-around time, and reduces project cost. On both HST and PSG, events with at least a 30% reduction in respiration for at least 10 sec associated with a 4% or greater oxygen desaturation will be scored as hypopneas. A recent study by the PI that compared scoring of PSGs at 5 sleep centers found an interclass correlation coefficient for AHI of 0.98 using these scoring criteria. To standardize scoring procedures at the sites, a manual that details scoring procedures will be developed. AHI will be calculated as the average number of apneas and hypopneas per hour of sleep on PSG and as the average number of those events per hour of recording on HST.

*Long-term follow-up.* Following the 3-month follow-up, participants will be scheduled for a follow-up with the sleep therapist every 6 months for the duration of their participation. Participants in the in-person arm will have in-person clinic appointments. Participants in the REVAMP arm will have phone clinic sessions.

*Controlling patient wait time.* We will monitor patient wait time throughout the protocol to compare the efficiency of REVAMP versus in-person management. REVAMP management will have a fixed schedule as detailed above. In order to match this timeframe, we will set a maximum limit to wait times for participants in the in-person group. Wait time for current in-person care varies widely across sleep centers. In order to enhance the applicability of our results to other sleep centers in the VHA and private sector, we will limit wait times of subjects in the in-person arm so that the initial clinic visit and sleep testing occur within one month of enrollment and the first follow-up clinic visit occurs within the first month of PAP treatment. This represents the current practice of

many private sleep centers. In order not to interfere with the routine clinical care at each site, schedules for research-related phone and in-person clinic sessions will be created. Finding similar PAP adherence and functional outcomes but differences in cost-effectiveness between REVAMP and in-person care when similar wait times are employed makes it likely that even more beneficial effects will occur when in-person wait times are longer. An advantage of the study's design is that we will be able to use our clinical and economic results to construct a decision model to assess the likely effect of delay due to waiting times.

Positive airway pressure treatment. Participants initiated on PAP treatment will be prescribed a SystemOne RemStar unit (Philips Respiration, Inc.) or an AirSense 10 unit (ResMed, Inc.) set at a pressure range of 4-20 cm H2O with in-line heated humidifier and wireless technology. The type of unit prescribed will be tracked. A strength of REVAMP is its ability to receive PAP information from both of these major manufacturers and display it on a common platform. The ability to use both manufacturers increases the generalizability of our study. Previous studies, including one by the PI, have validated the accuracy of the AHI determined by the PAP units of both manufacturers, i.e., the measure that will be used to assess treatment efficacy. The use of heated in-line heated humidification promotes adherence. The APAP units will be delivered to the participant by a therapist from a contracted home healthcare company. To create a patient-centered experience, the therapist will custom-fit the participant with the mask interface they prefer and explain how to operate and care for the equipment. All participants will be informed that their APAP unit will record their adherence to treatment and how well the treatment is working to correct their breathing disorder during sleep.

All practitioners will have access to the participant's daily APAP data at the manufacturer's HIPAA compliant, password protected web-site (EncoreAnywhere, Philips-Respiration, Inc or AirView, ResMed, Inc). Participants in the REVAMP arm and their practitioners will also be able to view the PAP data on the REVAMP website. When clinically indicated, adjustments to the APAP pressure range will be made either at the time of the in-person clinic visit or by entering this modification on the manufacturer's website that will reset the participant's APAP device by transmitting the information to the home unit via the wireless connection. Participants will be informed if the pressure range is adjusted. Subjects who unable to tolerate APAP or refuse treatment will be seen by a sleep physician for further evaluation and management.

Blinding of research personnel. Given the differences in management of the two groups, the research personnel cannot be blinded to a participant's group assignment. The practitioners delivering care will not be involved with scoring the HSTs and all of the participant questionnaires are self-administered. The practitioners will not have access to the patient satisfaction questionnaire results or to the data collected for Aims 2 and 3.

Formative evaluation (Aim 3). Through mixed quantitative and qualitative methods, we will explore patient- and *practitioner-centered* treatment acceptability and process of the two methods of OSA management. Quantitative: We will evaluate participant acceptance of web-based OSA management versus in-person management by comparing the between-group differences in process indicators, including attrition and therapeutic alliance. *We will evaluate practitioner acceptance of web-based OSA management versus in-person management by comparing the between-group differences in therapeutic alliance.* WAI-SR and CSQ-8 are patient-oriented scales which have been used widely as process indicators in research comparing delivery of treatment via telemedicine versus in-person format. Qualitative: We will conduct semi-structured phone interviews with a subset of up to 45 participants: 15 who complete the first 3-mo web-based intervention, 15 patients who complete the 3-mo in-person management, and 15 patients who drop out of either intervention group. Each patient will be interviewed over the phone by [name] who has extensive expertise in qualitative interviewing. The phone interviews will be conducted within one month of the participant completing either the first 3 months of PAP intervention or dropping out of the study. Phone interviews rather than in-person interviews were chosen for a number of reasons: the relatively non-sensitive nature of the interview topic; to decrease burden on patients; and to increase likelihood of successfully completing the targeted number of interviews. A semi-structured interview guide will be developed by [name] and revised in consultation with the research team. The interview guide will cover topics including: the participant's experiences with OSA; expectations going into treatment; attitudes, opinions, and experiences with treatment; reasons for dropping out (if relevant); perceived barriers and facilitators to continuing treatment; perceived therapeutic relationship with the provider; and suggestions for making treatment more patient-centered. We anticipate we will reach 'theme saturation' (where no new concepts emerge in the data) after completing approximately 12 interviews with patients from each group. Each interview will be audio-recorded and last between 30-60 minutes.

*To explore practitioner-level acceptability of REVAMP delivery of care compared with in-person delivery, as well as perceived barriers and facilitators to implementation of OSA management via REVAMP, we will conduct semi-structured phone interviews with the practitioners who provide OSA care and management for the study. As with the patient interviews described above, each practitioner will be interviewed over the phone by [name] using a semi-structured interview guide developed by [name] with input from the rest of the research team. The interview guide will cover topics including: the practitioner's background and prior experience with OSA treatment and management; experiences with barriers and facilitators to treating and managing patient's OSA using REVAMP; perceptions about patient's experiences with and attitudes toward receiving care via the REVAMP*

platform; and suggestions for improving delivery of OSA care via REVAMP. Practitioners will be interviewed after they have delivered care to a minimum of 20 participants in the REVAMP intervention group to ensure sufficient level of experience with REVAMP and with a variety of participants. Each interview will be audio-recorded and last between 30-60 minutes.

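### CES-D review and the primary care notice above 24 are specified only at baseline, although at least two further scores are scheduled by the month-3 endpoint visit

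*Combined protocol and SAP*

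**What the plan says.** **Baseline.** Under Eligibility criteria and enrollment, "Following completion of the baseline questionnaires, the CES-D score will be reviewed by a member of the research team" who has no part in delivering care, and the "primary care provider will be notified if the CES-D score is greater than 24, indicating the presence of severe depression". High scorers stay in the study, on the reasoning that those with OSA will be given APAP and that APAP helps depression.

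**Follow-up.** Table 2, titled "Data collection and action schedule for all participants", schedules the functional and quality-of-life set at baseline, 1 month and 3 months. Its footnotes define the set as "Functional & QOL questionnaires: FOSQ-10, ESS, SF-12, CES-D, and EQ-5D" and mark the 3-month entry as "performed every 3 months thereafter to the end of data collection".

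**Who sees the answers.** For the REVAMP arm: "The other questionnaire responses of the participants randomized to REVAMP management will be available to the practitioners performing the phone clinic evaluations". For the in-person arm: "None of the questionnaires they complete on the website will be shared with their practitioners". In-person participants also fill in the site's own routine questionnaires at clinic visits. The content of these is not given.

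**Other contact.** Primary care is told of enrollment and that "all clinically indicated care should continue to be provided". Both arms have clinical assessments at months 1 and 3, with extra contacts allowed when indicated. Long-term follow-up then provides a therapist contact every six months.

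**The concern.** The protocol sets its own standard: a CES-D above 24 means severe depression and calls for a named type of reviewer and a message to primary care. The trial then collects the same score repeatedly without saying that anyone will look at it for this purpose. A participant at 24 or below at baseline could rise above 24 at month 1 or later, and the plan could be followed to the letter with no response.

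That new crossing is the main gap. A score that stays high after a baseline notice matters less, because primary care has already been told.

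The reason given for keeping high scorers, that APAP should help, does not reach everyone. The protocol expects 20% of enrollees not to have OSA (356 × 0.20 = 71.2, about 71) and foresees some participants refusing or not tolerating APAP.

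What is at stake is participant safety, not the primary inference.

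**Working it through.** The plan states no count of follow-up CES-D scores, so there is no figure to reproduce. The check counts scheduled scores and then asks what the text requires for each.

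**Inputs**
- APAP set-up at week 8, 1-month assessment at week 12, 3-month assessment at week 20, then three-month steps (Table 2).
- At least nine months of post-treatment cost data on everyone (Sample size, and power).
- Two-year maximum follow-up (Statistical methods for Aim 2).
- Assumption: questionnaires continue as long as cost data are collected. The QALY instruments belong to the same questionnaire set, so this is reasonable.

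**Step 1: scheduled follow-up scores.** The times, in months after APAP start, are 1, 3, 6, 9, 12, 15, 18, 21 and 24.

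| Follow-up to | Scores at months | Follow-up scores | Reviewed share, with baseline |
|---|---|---|---|
| Month-3 endpoint visit | 1, 3 | 2 | 1 of 3 |
| Nine months post treatment | 1, 3, 6, 9 | 4 | 1 of 5 |
| Two years from enrollment | 1 to 21 | 8 | 1 of 9 |
| Two years from APAP start | 1 to 24 | 9 | 1 of 10 |

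For the third row: 104 − 8 = 96 weeks on APAP, and 96 ÷ (52/12) = 22.2 months, so month 21 is the last score.

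**Step 2: what is required at each score**

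| | Baseline | Follow-up |
|---|---|---|
| Assigned reviewer | Yes, outside care delivery | None stated |
| Cut-off for action | Above 24 | None stated |
| Notice to primary care | Yes | None stated |
| REVAMP practitioner | Can see the score | Can see the score; no stated duty to check it |
| In-person practitioner | Not shown | Not shown |

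**Step 3: scheduled contact after month 3.** If the six-month therapist interval runs from month 3, contacts fall at months 9, 15 and 21. Of the seven scores from month 6 to month 24, four (months 6, 12, 18, 24) have no scheduled contact in either arm.

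**Step 4: who is covered.** Table 2 is for all participants, and 356 are to be enrolled. About 285 are expected to have OSA (356 × 0.80 = 284.8). The remainder have no APAP start, so the timing of their follow-up scores is not defined. The documents give neither a completion rate for follow-up CES-D nor a rate of new scores above 24, so the number of participants affected cannot be calculated.

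**The case against.** The strongest reply is that this argues from silence. The available text has no adverse-event or safety-monitoring section, and Appendices 3 and 4 are cited but not included. A follow-up depression procedure could sit in any of these. The CES-D sentence also belongs to an enrollment paragraph, where one would expect only baseline to be covered. This stands as a limit on certainty. A reader might infer that the trial has no follow-up depression procedure at all; the documents do not support that.

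The second reply is that other safeguards exist: assessments at the time of the month-1 and month-3 scores, extra contacts as needed, the site's own questionnaires in the in-person arm, and continuing primary care. Entry also excludes a clinically unstable condition in the previous two months, with a new diagnosis of depression among the examples, and APAP is expected to improve mood. All of this lowers the likely number of new crossings. None of it requires anyone to look at the follow-up score, and the content of the site questionnaires is unknown.

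A reader might also infer that some participants have only one follow-up score, because Statistical methods for Aim 2 describes follow-up closing three months after the last enrollment (about week 13, after the week-12 score and before week 20). That reading would stop before the visit supplying the primary FOSQ-10 endpoint, and it conflicts with the nine-month statement. It should not be used to size this point.

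Finally, a reader might infer that the gap biases the trial's main comparison. The documents give no basis for that: the CES-D change is a secondary outcome, interpreted as hypothesis-generating.

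**Conclusion.** The concern holds as a patient-safety gap in the available text. The review, the cut-off and the notice are tied to baseline, while the same score is collected at least 2 more times by the month-3 endpoint visit, 4 times by nine months and 8 or 9 times by two years. No one is assigned to act on those later scores, and in the in-person arm the treating practitioners are not shown them.

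The counts rest on Table 2 timing and on questionnaires running as long as cost follow-up; 8 or 9 depends on when the two years start. They count scheduled forms, not people at risk. How many participants would be affected is unknown. The FOSQ-10 and adherence conclusions are not in question. Confidence is medium, because a follow-up rule may exist in parts of the protocol not available here. The change should be made, but it is not a reason to doubt the trial's main analysis.

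**What to change.** Extend the baseline rule to every scheduled follow-up CES-D in both arms: the same reviewer outside care delivery, the same cut-off (above 24) and the same notice to primary care, triggered by an automatic website flag.

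- **New crossings:** always notify when a score rises above 24 after a score of 24 or below, with no time cap. A cap of one notice per six months would miss, for example, a participant above 24 at month 1, at or below 24 at month 3 and above 24 again at month 6, because months 1 and 6 are only five months apart.
- **Persistent high scores:** repeat notices may be limited, since primary care already knows.
- **Records:** log notices by arm.
- **If a rule already exists elsewhere:** cite it beside the baseline rule. Nothing more is needed.

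**Cost.** Protocol wording and a website flag; the reviewer, cut-off and notice already exist. The load from new crossings is bounded. Each needs a low score followed by a high one, so with k follow-up scores plus baseline there are at most (k + 1)/2, rounded down: 1 by month 3 (k = 2), 2 by month 9 (k = 4), and 4 or 5 by two years (k = 8 or 9). Permitted repeat notices for persistent scores would be additional.

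**Downside.** The notice is a small co-intervention under the same rule in both arms. A month-1 notice could slightly affect the secondary month-3 CES-D change, and the log by arm lets that be described. Because notices go to primary care, website answers still do not reach in-person sleep practitioners through the study.
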